5.3.4 Adherence and Dose Modification

This is a pragmatic trial. Adherence will be documented by patients by providing a patient diary (see Supporting Documents) which shows the days on which they are supposed to take oral iron. This will be provided in a paper format. The research team will remind the patient to fill in their patient diary at 4 and 8 weeks. At the 12 week visit, the patient will be instructed to bring in their patient diary and pill bottle. A pill count will also be done to confirm adherence.

It is anticipated that ~ 30% of patients may not tolerate oral iron. The patient adherence diary instructions (see Supporting Documents) can be referred to for simple instructions (under point # 5) if the patient is having mild symptoms with the oral iron. Side effects may improve over the initial 1-2 weeks of oral iron. However, in some cases, patients may not be able to tolerate oral iron. Patients will be instructed to follow their planned schedule as prescribed. If they continue to have symptoms, patients will be instructed to step down in frequency (e.g. from daily to every other day; from every other day to two times per week; from two times per week to once per week) and to record how frequently they are able to take oral iron.

If patients are unable to take the oral iron at all, they will be continued to be followed as long as they are willing to continue and do not meet any criteria for withdrawal. Please refer to Section 10. Criteria for withdrawal from study.

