5.4.2.4 Week 12 Final Study Visit

Participants will be assessed in person/remotely (telephone/zoom/OTN) at Day 84 ± 7 days for the following assessment

- Adherence as determined by patient diary and pill count
- Side effect questionnaire
- FACIT-fatigue scale questionnaire
- Medication history (to confirm if any new or discontinued medications)
- Laboratory tests: CBC, reticulocyte count, ferritin, serum iron and TSAT
- Need for escalation in therapy: Y/N
 - Increase in oral iron regimen from every other day to daily
 - Intravenous iron
 - Transfusion
 - Visit to emergency department related to anemia

5.4.2.5 Week 13

Participants will be contacted by telephone or email at $7 \text{ days} \pm 3$ days after the Week 12 final study visit for assessment of adverse and serious adverse events.

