9.3.5 Reporting and Entry Timelines

Study investigators will report SAEs to the sponsor within the following timelines:

- All deaths and immediately life-threatening events, whether related or unrelated, will be recorded and reported to the sponsor within 24 hours of site awareness.
- Serious adverse events other than death and immediately life-threatening events, regardless of relationship, will be reported to the sponsor within 72 hours of site awareness.

Adverse event information will be entered into the CRF in a timely manner and **no later than 15 days** from the time the investigator becomes aware of the event.

Serious adverse event information will be entered into the CRF in a timely manner/**within 72 hours** from the time the investigator becomes aware of the event.

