10.1 Early Termination and Reasons for Withdrawal

Patients may find that they are not able to continue in the study due to intolerable side effects from the oral iron despite simple measures to address the side effects. Patients are permitted to withdraw consent at any time if they desire and will not undergo further trial investigations if they do so.

Additionally, patients who become pregnant during the course of the study will be stopped from using the study medications and withdrawn from the study. Other reasons for withdrawal include use of

intravenous iron, use of blood transfusion, any deviation from inclusion/exclusion criteria and serious adverse events (as described in section 9.3).

Participants withdrawing from the study should be contacted by the study research team requesting a final visit and to follow up with any unresolved adverse events. Once withdrawn from the study, no further study procedures or evaluations should be performed, or additional study data collected. However, every effort should be made to obtain permission to document the reason for withdrawal and to collect participant outcomes, such as survival data up to the protocol-described end of participant follow up period, where possible. Any data collected prior to the withdrawal of consent may be retained and used by the sponsor. If the patient withdraws from the study, the research team will notify the patient's referring physician.

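### Sections 10.1 and 10.2 contradict each other on data collection after withdrawal, and neither schedules new adverse events, the side effect questionnaire or the Week 13 contact for a patient withdrawn after an SAE

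*Combined protocol and SAP*

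**What the plan says.** Section 10.1 gives the reasons for withdrawal from the study. Besides pregnancy, intravenous iron, transfusion and eligibility deviations, it lists "serious adverse events (as described in section 9.3". It then states: "Once withdrawn from the study, no further study procedures or evaluations should be performed, or additional study data collected". The same paragraph has two softer provisions. Withdrawn patients are contacted, "requesting a final visit and to follow up with any unresolved adverse events", and with permission the team tries to "collect participant outcomes, such as survival data up to the protocol-described end of participant follow up period, where possible".

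Section 10.2, which is devoted to withdrawn participants, asks them to go on with the quality of life measure and the laboratory tests. Its stated reason is that outcomes after stopping the intervention are needed to judge feasibility.

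On which SAEs are meant, section 9.1.5 joins seriousness, by AND, to the attending physician's view that the event may be linked to participation or to the assigned arm. Section 9.3.5, which lies inside the section that 10.1 cites, says: "Serious adverse events other than death and immediately life-threatening events, regardless of relationship, will be reported to the sponsor within 72 hours".

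Three other places bear on follow-up:

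- Section 5.3.4 keeps patients who cannot take any iron in the study: "they will be continued to be followed as long as they are willing to continue and do not meet any criteria for withdrawal".
- Section 10.0 ends follow-up at 12 weeks or at escalation of therapy and does not mention SAEs.
- Section 5.4.2.5 (Week 13) sets a contact 7 ± 3 days after the "Week 12 final study visit for assessment of adverse and serious adverse events".

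**The concern.** An SAE may be a reason to reconsider study treatment. Ending data collection is a separate decision, and the plan joins the two for SAEs while keeping them apart in 5.3.4 for patients who merely stop taking iron. A patient with an SAE is one whose later safety record is most wanted, and section 9.4 provides no data monitoring board, so safety information depends on follow-up of individual patients.

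Three things are at stake. The first is the adverse event record after withdrawal. The second is the side effect outcome at 4, 8 and 12 weeks (item 14 in 3.4 and 7.2). The third is whether 4-week and 12-week hemoglobin exists for everyone in the intention-to-treat analysis of 8.2. With two sites and two contradictory instructions, the data kept could depend on which section a site happens to follow.

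**Working it through.** The plan gives no figure on this point, so the check is mainly a comparison of text.

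**Step 1. What each section keeps after withdrawal.** Scheduled items are from 5.4.2 and Appendix C.

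| Scheduled item | Section 10.1 | Section 10.2 |
|---|---|---|
| Blood tests, including hemoglobin at weeks 4 and 12 | Stops | Requested |
| FACIT-fatigue at weeks 4, 8 and 12 | Stops | Requested, as the quality of life measure |
| Side effect questionnaire | Stops | Not named |
| AE still open at withdrawal | Followed up | Not named |
| New AE or second SAE | Stops, unless found at the requested final visit | Not named |
| Week 13 AE/SAE contact | Stops | Not named |
| Outcomes such as survival | With permission, where possible | Not named |

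The first two rows are a direct contradiction. The rows for the questionnaire, new events and Week 13 are a gap under both sections. Survival, the only outcome 10.1 names, is not among the outcomes in 3.4 or 7.2.

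**Step 2. Which SAEs trigger the rule.** If 9.1.5 governs, only events perceived as possibly related count, and the rule then falls on suspected reactions to the intervention. If 9.3.5 governs, an unrelated hospital admission could count too. Section 10.1 points to 9.3, while 9.2.3 points to 9.1.5. The text does not settle it.

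**Step 3. Whether withdrawal is automatic.** For pregnancy, 10.1 says outright that the patient is stopped and withdrawn. For SAEs it only includes them in a list of reasons. Section 10.0 does not list them as an end of follow-up, while 5.3.4 makes continued follow-up conditional on meeting no withdrawal criterion.

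**Step 4. Which state a patient is in.** Section 10.2 speaks of withdrawn participants in its heading, of patients off the intervention in its rationale, and of patients who withdrew consent in its contact procedure. These are three different states, with different implications for what may be collected.

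**Step 5. How many patients.** No SAE rate is given, so the rate p is an assumption. Expected number = 52 × p; chance of at least one = 1 − (1 − p)^52.

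| Assumed p | Expected of 52 | Chance of at least one |
|---|---|---|
| 1% | 0.5 | 41% |
| 2% | 1.0 | 65% |
| 5% | 2.6 | 93% |
| 10% | 5.2 | 99.6% |

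For scale, section 8.1 wants 52 enrolled and at least 36 completing to 13 weeks, so it tolerates 52 − 36 = 16 losses. The 36 and 52 match Table 2 (SD 5, margin 5, true difference 0, one-sided 5%, 90% power): 18 per arm gives 36, and 36/0.70 = 51.4, which becomes 52. The assumed SAE losses fit inside that allowance, so power is not the issue. What matters is which data go missing, and whether a patient followed under 10.2 after an SAE counts toward the 36, which the plan does not say.

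**The case against.** The best defence is that 10.1 should not be read alone. Section 10.2 is the specific section for withdrawn participants and requests blood tests and the fatigue scale. Section 10.1 itself keeps a final visit and open adverse events, and its reference to survival is an example, so other outcomes could be collected under it. Section 9.1.1 also sets an adverse event recording window up to one week after the final study visit, with no stated exception for withdrawn patients. Risk is described as low in 9.1.2, and few SAEs are likely.

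Much of this stands, and it rules out several stronger readings that a reader might infer:

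- **That hemoglobin follow-up stops at the first SAE.** Section 10.2 requests the laboratory tests, so this is a contradiction with a possible loss, not a certain one. Nor does the text say that withdrawal at a first SAE is automatic.
- **That all safety follow-up stops.** The final visit and the follow-up of open events remain.
- **That any SAE counts, related or not.** This is one of two readings, because 9.1.5 requires perceived relatedness.
- **That the rule biases the hemoglobin comparison by removing patients admitted for worsening anemia.** Transfusion, intravenous iron or an anemia-related emergency visit already ends follow-up through the separate escalation rule in 5.4.2.2 and 10.0.
- **That a shift in the arm mean can be put in g/L.** The documents give neither an SAE rate nor a hemoglobin deficit for such patients, and the sum would assume that the hemoglobin is lost despite 10.2.

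What the defence does not answer is the gap. No wording in 10.1 or 10.2 schedules the side effect questionnaire, new adverse events or the Week 13 contact once a patient is withdrawn. The window in 9.1.1 does not close it, because 10.1 forbids further data and does not say whether the visit held at withdrawal is the final study visit.

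**Conclusion.** The point holds as a contradiction and a gap in the rules for data collection. A site that follows 10.1 loses later safety data, and possibly week 12 hemoglobin, in patients withdrawn for an SAE. A site that follows 10.2 keeps the blood tests and fatigue scale but still has no instruction for new safety events. Which SAEs bring a patient under the rule is undefined.

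The size cannot be stated from the documents. The range of about 0.5 to 5 patients rests on assumed SAE rates of 1% to 10% and on every such patient being withdrawn, which the text does not require. The primary outcome, time to enroll 52 patients, is not affected. It should still be changed, because the data at risk are safety data and part of the intention-to-treat set.

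**What to change.** Reconcile sections 9.1.5, 9.3.5, 10.0, 10.1 and 10.2, as follows:

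1. Define stopping study iron, withdrawal from follow-up and withdrawal of consent as separate states, and say what is collected in each.
2. State that, whatever is decided clinically about study iron, an SAE alone does not end data collection. The scheduled laboratory tests, FACIT-fatigue scale, side effect questionnaire and AE/SAE contacts continue through Week 13 unless consent is withdrawn.
3. Say whether an SAE in 10.1 is meant in the sense of 9.1.5 or of 9.3.5.
4. Say how such patients count toward the 36 completers in 8.1, and how the escalation rule in 10.0 applies when an SAE also involves escalation.

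This concerns data collection only. It proposes no rule on study iron after an SAE and does not ask for a withdrawal criterion to be deleted. The cost is a protocol wording amendment and, for the few patients affected, contacts and tests that are already in the schedule.

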10.2 Data Collection and Follow-up for Withdrawn Participants

Patients will be asked to continue with follow-up quality of life assessment and laboratory tests. It is important to continue to follow these patients and capture outcomes that occur once they have discontinued study intervention to determine feasibility. Through telephone calls and emails, every effort will be made to obtain permission to document the reason participants withdrew consent and to continue collecting the quality of life assessments and laboratory values previously mentioned. Patients who have completed at least 90% of the prescribed doses will be included in the per-protocol analysis.

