7.2 Secondary outcome assessments

Feasibility

1. Proportion of eligible patients consenting to participate

$$\frac{\# \text{ meeting eligibility criteria} - \# \text{ in whom consent not obtained}}{\# \text{ meeting eligibility criteria}}$$

2. Proportion of consenting patients receiving the allocated treatment

consenting to treatment - # not administered allocated treatment
consenting to treatment

3. Proportion of treated patients completing 4 week and 12 week laboratory tests

completing 100% of 4 week and 12 week lab tests
consenting to treatment

4. Proportion of treated patients completing 4 week, 8 week and 12 week side effect questionnaire

completing 100% of 4 week, 8 week and 12 week side effect questionnaire
consenting to treatment

5. Proportion of treated patients completing 4 week, 8 week and 12 week FACIT-fatigue scale

completing 100% of 4 week, 8 week and 12 FACIT-fatigue scale
consenting to treatment

6. Proportion of treatment doses taken as per protocol based on pill count

$$\frac{\text{total # of doses} - \text{# of missed doses}}{\text{total # of doses}}$$

7. Proportion of treated patients taking at least 90% of their prescribed doses

$$\frac{\text{# of patients taking at least 90% of prescribed doses}}{\text{total # of treated patients}}$$

8. Proportion of treated patients requiring a step down in therapy

$$\frac{\text{# of patients requiring step down in therapy}}{\text{total # of treated patients}}$$

Clinical/Safety

9. Hemoglobin increment at 4 and 12 weeks is defined as the 4 or 12 week hemoglobin value minus the baseline hemoglobin value

10. Proportion with complete hemoglobin response defined as hemoglobin greater than or equal to 120 g/L in women; and 130 g/L in men at 4 weeks and 12 weeks

11. Change in reticulocyte count at 4 and 12 weeks defined as the 4 or 12 week reticulocyte count minus the baseline reticulocyte count

12. Change in ferritin, serum iron and TSAT at 12 weeks defined as the value at 12 weeks minus the baseline value

13. Quality of life (FACIT-fatigue scale) at 4, 8 and 12 weeks

14. Proportion with side effects and type of side effects at 4, 8 and 12 weeks as determined by the oral iron side effect questionnaire
15. Proportion of patients who stop taking oral iron due to side effects at 4 and 12 weeks

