9.1.2 Expected adverse events with ferrous sulfate

Side effects of oral iron supplementation include constipation, nausea, diarrhea, abdominal pain, vomiting, heartburn, flatulence and dark stools.^{8,35} When compared to placebo in randomized controlled trials, ferrous sulfate had an increased incidence of gastrointestinal (GI) side effects with an OR 2.32 (95% CI 1.74-3.08). The proportion of patients with GI side effects was 35% (range 10-90%) in the ferrous sulfate arms compared with 22% (range 0-69%) in the placebo arms. The most common side effects were constipation, nausea and diarrhea with pooled estimates of incidence of 12%, 11% and 8% respectively.³⁵ Additional side effects included abdominal pain, vomiting, heartburn, flatulence and dark stools.

Overall, the risk to patients enrolled in this study is anticipated to be low, as 1) patients with IDA would normally be treated with oral iron; 2) patients with a prior history of intolerance to oral iron will be excluded; 3) exclusions include patients with baseline gastrointestinal disease such as inflammatory bowel disease; 4) patients will be monitored for side effects throughout the study; and 5) side effects stop immediately with stopping oral iron with no long term sequelae.

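### Sections 10.1 and 10.2 conflict on what is collected after withdrawal, and neither keeps the side effect questionnaire, so patients who withdraw for intolerance have no outcome 14 data at later visits

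*Combined protocol and SAP*

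**What the plan says.** Section 10.1 foresees intolerance as a way out of the study: "Patients may find that they are not able to continue in the study due to intolerable side effects from the oral iron". For anyone who withdraws it sets a general bar: "Once withdrawn from the study, no further study procedures or evaluations should be performed, or additional study data collected". It then softens this by asking that permission be sought to record the reason and to collect participant outcomes, with survival as its example. The team is to contact the patient, "requesting a final visit and to follow up with any unresolved adverse events". Earlier data are safe: "Any data collected prior to the withdrawal of consent may be retained and used by the sponsor".

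Section 10.2 takes a different line: "Patients will be asked to continue with follow-up quality of life assessment and laboratory tests". It repeats the same two items when it describes calls and emails made "to continue collecting the quality of life assessments and laboratory values previously mentioned". The side effect questionnaire appears in neither sentence, and no other section adds it.

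Outcome 14 in section 7.2 is "Proportion with side effects and type of side effects at 4, 8 and 12 weeks as determined by the oral iron side effect questionnaire". It names no other source and no denominator, and section 8.2 gives no rule for missing forms. Section 9.1.2 states that "side effects stop immediately with stopping oral iron with no long term sequelae".

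**The concern.** The secondary objective (3.2) joins effectiveness with keeping side effects low, and 2.1.6 asks for side effects to be documented with care. The plan expects about 30% of patients not to tolerate oral iron (5.3.4) and 30% to drop out (5.1). Loss of patients for reasons tied to the side effect outcome is therefore foreseeable. Section 10.2 stresses capturing outcomes after patients stop, yet its list leaves out the form closest to the reason many would stop.

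At stake is the tolerability comparison that the pilot hands to the definitive trial. If one arm loses more patients to side effects, the visit proportions describe mainly those who tolerated the tablets, and that arm's burden is understated.

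**Working it through.** **1. The two sections side by side.** Under 10.1, nothing further is collected after withdrawal, apart from adverse event follow-up, the reason, and outcomes for which permission is obtained. Under 10.2, fatigue scale and laboratory data continue. They disagree on the default for every outcome. On the side effect questionnaire they give the same practical answer: neither names it.

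**2. What each patient contributes to outcome 14.**
- Withdraws before week 4: nothing. A week 1 form may exist under 5.4.2.1, although Appendix C does not mark it, but week 1 is not an outcome 14 time point.
- Withdraws between weeks 4 and 8: week 4 only.
- Withdraws between weeks 8 and 12: weeks 4 and 8.
- Stops tablets but stays in the study (5.3.4): all visits.

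**3. Inputs for size.** The plan states no figure for this point. From the documents: 26 per arm (5.1); 35% with GI side effects on ferrous sulfate, range 10–90% (2.1.6); 30% dropout (5.1, 8.1). The dropout figure is used consistently: 52 × 0.70 = 36.4, in line with the 36 in section 4.0. The number of affected patients who withdraw is not given, so it is assumed and varied.

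**4. One arm.** 0.35 × 26 = 9.1, taken as 9 ever affected. If *k* of them withdraw before a visit and the rest still report symptoms, the proportion among responders is (9 − *k*)/(26 − *k*):
- *k* = 0: 9/26 = 34.6%
- *k* = 2: 7/24 = 29.2%
- *k* = 4: 5/22 = 22.7%
- *k* = 6: 3/20 = 15.0%

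**5. What the missing forms themselves do.** Take *k* = 4. If all four leavers returned later forms showing no symptoms, as 9.1.2 implies, the visit figure would be 5/26 = 19.2%. Missing forms therefore move the visit proportion up, by 22.7 − 19.2 = 3.5 points. The gap of 34.6 − 22.7 = 11.9 points is between a cumulative proportion and a visit proportion. Only a cumulative measure closes it; later repeat forms would not.

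**6. Range at 30% dropout.** Let *p* be the proportion ever affected, *d* = 0.30, and *s* the share of dropouts who leave for side effects and give no form (assumed). The responder proportion is (*p* − *ds*)/(1 − *ds*). For *p* = 35% it is 35%, 30%, 24%, 16% and 7% at *s* = 0, 0.25, 0.5, 0.75 and 1. For *p* = 90% it runs only from 90% to 86%. For *p* = 10%, *s* cannot exceed one third.

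**7. Between arms.** If 9 of 26 are ever affected in each arm, and 4 leave the daily arm and none the other, the visit proportions are 5/22 and 9/26, an artefact of 11.9 points. The 95% half-width for such a difference is 1.96 × √(0.227 × 0.773/22 + 0.346 × 0.654/26) = 1.96 × 0.129, or about 25 points.

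**The case against.** The other side has real force.

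- **Intolerance is recorded elsewhere.** Outcome 15 counts patients who stop iron for side effects, and outcome 8 in 3.4 counts step-downs for that reason. Adverse events are sought at every contact (9.2.5) and related ones are coded (9.1.1). The reason for withdrawal is requested. An arm that loses more patients to side effects would look worse on outcome 15. This stands, and it is why the effect is limited to outcome 14. It does not supply the type of side effect on the same instrument. Follow-up at withdrawal covers unresolved events, and many may already have resolved if 9.1.2 is right.
- **Most intolerant patients may never withdraw.** Under 5.3.4 they step down first, and those who cannot take iron at all are followed if willing and no withdrawal criterion is met. This stands and may keep the number small.
- **The form may already be intended.** The content of the withdrawal visit is not listed, the week 12 visit does include the questionnaire, and the permission clause in 10.1 could be read to cover it. That is possible, but nothing says so. The form's recall period is in supporting documents not included here.
- **The stakes are modest.** The primary outcome is time to enroll 52, and 8.2 plans no test of outcome 14. This stands.

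A reader might infer that patients who leave for intolerance vanish from the side effect record, or that the missing forms alone pull 35% down to 23% and bias the trial by 12 points towards daily dosing. The documents support neither. Data collected before withdrawal are kept, and step 5 shows that the fall comes from comparing cumulative with visit proportions. No section supports a four-to-none split between arms. Section 2.1.5 reports no difference in side effects or adherence between intermittent and daily dosing, though from very few trials.

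**Conclusion.** The point holds in a limited form. Sections 10.1 and 10.2 conflict, and neither keeps the only instrument for outcome 14. Patients who withdraw for intolerance have no outcome 14 data at later visits, and none at all if they leave before week 4. Given visit-specific reporting and the statement in 9.1.2, visit proportions understate the cumulative burden in an arm that loses more patients to intolerance.

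The size cannot be known from the documents. The contrast of 35% ever affected with 23% among responders is an upper bound for four affected leavers. It assumes a responder-only analysis, no form from the leavers at that visit, and persisting symptoms in the other five. Any between-arm artefact of that order would sit well inside the sampling error of a pilot this size. The reason to act is that the change is cheap and the definitive trial could inherit the gap.

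**What to change.** 1. Reconcile 10.1 and 10.2: state what is collected after withdrawal and with what permission, and separate stopping tablets from leaving the study.
2. With the patient's permission, complete the side effect questionnaire at the withdrawal contact that 10.1 already plans, covering the time on tablets since the last contact.
3. Add to outcome 14 a cumulative summary: any side effect from first tablet to week 12 or withdrawal, on all treated patients. Use every form, including week 1, and count documented stopping or withdrawal for side effects as an event. Align Appendix C with 5.4.2.1 on the week 1 form.
4. State the denominator and the handling of missing forms for the visit proportions.

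The cost is one existing form at a planned contact, one extra summary line and a short text edit. Treatment is unaffected. Some patients who withdraw consent will decline the form, and the cumulative measure partly overlaps outcome 15.
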